In summary, oropharyngeal colonization is extremely common among patients with *S. aureus* infections and there are mounting data suggesting that decolonization regimens that fail to decolonize the oropharynx leave behind a critical reservoir of *S. aureus*. This reservoir can then serve as a persistent source of *S. aureus* colonization that can be the nidus for subsequent infections. Because recurrence rates of *S. aureus* skin infection are so high, there is an urgent need to study the efficacy of oropharyngeal decolonization regimens for *S. aureus* in children before they can be used in more comprehensive decolonization regimens.

Experimental Design and Methodology (See General Instructions for page limitations/recommendations)

This investigation is a randomized, prospective, multi-center, placebo-controlled clinical trial to examine eradication of *S. aureus* from the oropharynx of children age 5-17 who recently experienced an SSTI and have proven oropharyngeal *S. aureus* colonization. We will compare eradication of oropharyngeal *S. aureus* colonization among those randomized to oral chlorhexidine (CHG) oral rinse compared to those randomized to placebo. Our investigative team has experience in *S. aureus* treatment and prevention, Pediatrics, Infectious Diseases, Emergency Medicine, Microbiology, Molecular Biology, Infectious Diseases Epidemiology, and Health Services Research. We have ample experience enrolling subjects in the Pediatric Emergency Department (PED) setting. Over the last 6 years, [name] group has enrolled over 3,500 subjects into epidemiologic studies and clinical trials focused on infectious diseases, a third of which were children.^{9,17,18,75-85} Drs. [name] and [name] have collaborated on a National Institutes of Health (NIH) multi-center clinical trial comparing TMP-SMX and clindamycin for the treatment of skin and soft tissue infections in children and adults in the ambulatory care setting.⁸⁶ [name] has worked with [name] for over seven years on multiple federally-sponsored investigations including clinical trials sponsored by the NIH, Centers

for Disease Control and Prevention (CDC), and the Agency for Healthcare Research and Quality (AHRQ).^{18,75,77-82} Starting early 2015, [name] will lead a team of research assistants whose mission is to help identify patients who are eligible for clinical trials and connect them with the appropriate recruitment team. The study activities and milestones are outlined in Figure 2.

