- Receipt of systemic antibiotics in the prior 28 days.
- Plans for administration or likely receipt of systemic antibiotics in the next 28 days (e.g., if the patient suffers from recurrent infections such as otitis media or has a planned surgery that requires prophylactic antibiotics).
- Plans for hospitalization or likely hospitalization in the next 28 days (e.g., if the patient suffers from recurrent infections).
- Any of the following in the prior 6 months: hemodialysis, peritoneal dialysis, central venous catheter placement, and systemic chemotherapy for cancer, any immunocompromising condition. These criteria ensure that subjects enrolled with have CA-*S. aureus* infections and are likely colonized with USA300 *S. aureus*, the most common cause of SSTIs in the U.S.
- Previous participation in the study.

All patients who participate in the clinical trial will be followed for 28 days for the purpose of determining which subjects achieve and maintain eradication. Participants will be enrolled regardless of race, ethnicity, or gender. While younger children commonly suffer from SSTIs, for this investigation we will only enroll children 5 years of age and older, as younger children may not be able to gargle. In a pilot study of 64 children from a general dentistry practice asked to gargle, among the 12 children ages 3-4, only 2 (17%) could complete a 30 second gargle, whereas 51/52 (98%) of those ages 5-8 could gargle successfully ([name], personal correspondence).

To recruit subjects, study coordinators will screen the PED three times daily. During screening, they will

Baseline visit

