Subjects will also be swabbed for *S. aureus* and MRSA colonization at the anterior nares and oropharynx. Testing will be performed using two methods: direct microbiology cultures and rapid molecular testing. Microbiologic cultures will be performed by culturing swabs from sites taken to identify *S. aureus* and MRSA carriage will be transported to the research microbiology laboratory at LA BioMed at Harbor-UCLA and plated within 24 hours of collection. Swabs will be processed for *S. aureus* using blood agar and CHROMagar plates for rapid identification of *S. aureus* and MRSA. All *S. aureus* and MRSA isolates will be banked for pulse-field typing, determination of SCCmec type, and presence of the PVL locus (*lukF-PV* and *lukS-PV*). Rapid molecular testing will be performed using the GeneXpert MRSA/SA platform, which is currently available at our site.

Upon confirmation of eligibility, the study coordinators will call the pharmacy to randomize the participant and obtain the oral rinse. The randomization assignment list will be generated in advance by pharmacy. Randomization procedures by an assignment list will be prepared by a computer method. To ensure adequate balance of subjects between the CHG and placebo groups, treatment allocation will be assigned using a random number generation with randomization of blocks of four subjects each. The randomization list will be kept by the pharmacy and treatment allocation randomization will not be shared with either the study staff or patients. The research pharmacists will dispense the appropriate oral rinse to the participant and their parent/guardian. Placebo will be created using the inert vehicles components of CHG, as has been done previously.⁸⁹ Participants and their parent/guardian will be given detailed instructions on the use of the oral rinse both verbally and in a handout in either English or Spanish as preferred by the participant and their parent/guardian.

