WGS sequencing will addresses several hypothesis in those subjects randomized to CHG oral rinses, specifically: a) strains that are found in the oropharynx at end of treatment (Day 7) will be identical genetically to those at baseline and not represent acquisition of new *S. aureus* strain; b) recolonizing *S. aureus* strains at Day 28 among subjects successfully eradicated at Day 7 will represent (re)colonization with the original isolate that colonized the nasopharynx from the same individual (if present at baseline) or a new *S. aureus* strain not present at baseline and; c) nasal isolates found at baseline and follow up will be identical to synchronously identified oropharyngeal *S. aureus* isolates.

Based on data in older adults,¹⁹ we estimate that of the 30 subjects randomized to the CHG arm, 50% will be decolonized, leaving 15 subjects who will be *S. aureus* positive at the oropharynx at the end of treatment. Based on data of recolonization after decolonization in which recolonization can occur after the decolonization regimen is completed,¹⁰ we estimate that a 10% increase in colonization will be seen at Day 28, i.e., 18 subjects will be oropharyngeally colonized with *S. aureus* at Day 28. Thus, we anticipate we will have results in 33 pairs of oropharynx isolates (15 between baseline and Day 7, and 18 between baseline and Day 28, for a total of 66 isolates total). Additionally we will conduct whole genome sequencing on baseline nasal *S. aureus* isolates associated with the subsequent oropharynx isolates identified at Day 7 and/or Day 28. Based on previous data suggesting that ~45% of those colonized at the oropharynx will be colonized at the anterior nares,^{18,46,95} we estimate an additional 30 (45% x 66) nasal *S. aureus* isolates from baseline and follow-up will be present synchronously with oropharyngeal isolates.

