This investigation is limited as it is a single center study. However, our center serves a ethnically and socioeconomically diverse population and findings from our investigations have been comparable to similar investigations in other populations.^{18,96,97} Our intervention is also singular in decolonization efforts (oropharynx only). However, no investigation has looked at the effect of *S. aureus* eradication on the oropharynx in children, so the addition of other decolonizing agents would prevent us from determining the efficacy of CHG oral rinse. Additionally, our trial is a “proof of principle” study that is required prior to a more comprehensive trial on *S. aureus* decolonization as a means for SSTI prevention. Finally, we are not performing WGS typing on all colonizing *S. aureus* isolates at all study time points, as it is known that *S. aureus* can colonize not only the nares and oropharynx, but the axilla, inguinal fold, perirectal area, vagina, and areas of skin that have lost integrity.^{42,47,98,99} However, the extra cost of testing these sites for possible sources of *S. aureus* that can later recolonize the oropharynx would be extremely expensive. Thus we chose just to perform testing in sites in which *S. aureus* is most commonly found (nares, oropharynx).

Future Directions

Investigation on prevention of recurrent *S. aureus* SSTI have been extremely disappointing, suggesting more comprehensive decolonization regimens need to be developed, especially those that focus on sites of colonization not previously targeted in clinical trials. Our investigation will be the first study to examine the efficacy of CHG to eradicate *S. aureus* from the oropharynx of children. [name] and his team provide ample experience in the area of MRSA infection and colonization, infectious disease expertise, clinical trials, and pediatrics. Besides the aims addressed for this investigation, our team is poised to address future aims related to *S. aureus* decolonization efforts and SSTI recurrences by generating information on the efficacy of CHG. In summary, the results of this investigation will provide the critical foundation for the development of future clinical trials. Data generated from our investigation will further investigative work on prevention of recurrent *S. aureus* SSTIs, which remain an extremely common and vexing clinical problem for clinicians, and more importantly, patients.

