Patients at Harbor-UCLA Medical Center come from a diverse racial and ethnic background, with approximately 51% Hispanic, 26% Caucasian, 18% African-American, and 6% "other" (largely Asian and to a lesser extent, mixed race). Two hundred and forty patients are anticipated to be enrolled over 18 months to randomize 60 subjects. Subjects constitute a cross-section of pediatric patients either presenting to our health care facilities that had a history of a skin and soft tissue infection, and will thus consist of pediatric patients age 5-17 and both genders.

There are risks to subject confidentiality, which will be mitigated by all PHI information being kept at the individual site with secure locked filing cabinets and/or on a password-protected computer file. This likelihood of subject confidentiality being broken is minimal. Risks to confidentiality will be protected by keeping all study data in a locked office with access restricted to study personnel. All identifiers will be removed and destroyed when data is logged into an Access database. We will protect against psychological risk to the patient by including an educational discussion with the patient including the nature of bacterial colonization, the risks, current treatments, the lack of acceptance of routine treatments, and the ability to attempt treatment in the case of recurrent infections. If a subject suffers psychological harm, they may contact the Principal Investigator and they will discuss further options. Subjects will be told that their information will not be shared with any persons except for study personnel unless the subject provides

permission. Finally, subjects will be told they can choose not to participate in the study or end their participation at any time without any effect on the care they will receive from their treating physicians or at their treating institutions.

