Risks associated with study medication is believed to be minimal. Chlorhexidine-gluconate (CHG) oral rinse is an FDA-approved medication for the treatment of gingivitis. The known side effects of oral CHG oral rinse include staining of teeth and other oral surfaces, an increase in calculus formation; and an alteration in taste perception.¹⁰⁰ All of these potential side effects are transient, reversible, or preventable with education and standard oral hygienic practices (e.g., tooth brushing). All subjects will be educated on the proper use of the oral rinse. Subjects will be asked to report any adverse events to study personnel and to stop the use of the oral rinse if any severe side effects develop (swelling, pain, etc.). Staff will also be able to counsel subjects about the risks and benefits of the oral rinse to decolonize the oropharynx. Study personnel will also have cell phones, which subjects can call to ask questions about the study, use of the intervention oral rinse, and report adverse events. Subjects that report serious adverse events or other medical needs will be referred to the Harbor-UCLA Medical Centers' Pediatric Emergency Department.

An Investigational New Drug (IND) application will not be required, as a clinical investigation of a marketed drug is exempt from IND requirements if all of the criteria for an exemption in § 312.2(b) are met:

- The drug product is lawfully marketed in the United States.
- The investigation is not intended to be reported to FDA as a well-controlled study in support of a new indication and there is no intent to use it to support any other significant change in the labeling of the drug.
- In the case of a prescription drug, the investigation is not intended to support a significant change in the advertising for the drug.
- The investigation does not involve a route of administration, dose, patient population, or other factor that significantly increases the risk (or decreases the acceptability of the risk) associated with the use of the drug product (21 CFR 312.2(b)(1)(iii)).
- The investigation is conducted in compliance with the requirements for review by an IRB (21 CFR part 56) and with the requirements for informed consent (21 CFR part 50).
- The investigation is conducted in compliance with the requirements of § 312.7 (i.e., the investigation is not intended to promote or commercialize the drug product).

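### Fixed blocks of four, stated in the protocol and not withheld from staff, make later allocations predictable if earlier arms become known, and the protocol gives the chlorhexidine arm visible items that could make them known

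*Combined protocol and SAP*

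**What the plan says.** Under Baseline visit (Experimental Design and Methodology), once eligibility is confirmed, "the study coordinators will call the pharmacy to randomize the participant and obtain the oral rinse". The pharmacy generates the list in advance and keeps it, and allocation is not shared with study staff or patients. On the list itself, "treatment allocation will be assigned using a random number generation with randomization of blocks of four subjects each". No stratification and no variation in block size are described, and nothing says that the size is withheld from staff. The placebo is made from the inert vehicle components of the chlorhexidine (CHG) rinse; matching of taste, color or bottle is not stated.

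Allocation is 1:1: Aim 3 speaks "of the 30 subjects randomized to the CHG arm", out of 60 randomized. On pace, Human Subjects says: "Two hundred and forty patients are anticipated to be enrolled over 18 months to randomize 60 subjects". On sites, Limitations says: "This investigation is limited as it is a single center study". The opening of Experimental Design says instead: "This investigation is a randomized, prospective, multi-center, placebo-controlled clinical trial". I take the single-center statement as the working one, since recruitment is described at one emergency department.

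Human Subjects lists the known effects of the rinse as "staining of teeth and other oral surfaces, an increase in calculus formation; and an alteration in taste perception". Tolerability and adverse events are surveyed at Visit 2 (Day 7).

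Two passages treat the arms differently in ways staff could see. Baseline visit provides a new soft toothbrush to the CHG arm and says that the other arm, there called usual care, gets none of the items just listed. Human Subjects gives additional verbal and written instruction on the rinse to the intervention arm only, whereas Baseline visit elsewhere gives detailed instructions to all participants.

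**The concern.** In a block of four with two children per arm, the last one or two allocations follow from the earlier ones. A coordinator who knows the block size and has learned the earlier arms would know the next assignment before calling the pharmacy.

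Two things are then at stake. The first is selection. Some entry criteria rest on judgment, such as the ability to gargle or "Plans for administration or likely receipt of systemic antibiotics in the next 28 days", and coordinators also influence who is approached. The second is the blind. Identifying both children of one arm in a block identifies the other two, even if those two report nothing. The documents do not assign separate, shielded staff to the Day 7 swab or to the adherence, tolerability and adverse-event surveys that Aim 2 uses.

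**Working it through.** The plan states no predictability figure, so there is none to reproduce.

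**Inputs.** Block size 4, allocation 1:1, 60 randomized (so 60/4 = 15 blocks), 18 months of enrollment (about 548 days / 60 = 9.13 days per randomized child), and staff surveying tolerability at Day 7. The probability q that an earlier child's arm is known is not in the documents. It is an assumption and is shown as a range.

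**1. All earlier arms known (q = 1).** There are 6 balanced sequences of four. In 2 of them (AABB, BBAA) the third and fourth places are determined; in the other 4 only the fourth is.

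- Certain allocations per block: (2×2 + 4×1)/6 = 8/6 = 1.333, or 1.333/4 = 33.3%. Over 15 blocks this is 20 of 60.
- Best-guess rate by place: 1/2, 2/3, 2/3, 1. The mean is 2.833/4 = 17/24 = 70.8%, or 42.5 of 60, against 30 of 60 under concealment.
- One third is an average. Each block has one or two certain places, so the trial total is 15 + Binomial(15, 1/3): possible range 15 to 30 (25% to 50%), central 95% 17 to 24, and a 38% chance of more than 20.

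**2. Each earlier arm known independently with probability q.** The third place is certain with probability q²/3 and the fourth with probability q². The share is (q²/3 + q²)/4 = q²/3.

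| q | certain share |
|---|---|
| 0 | 0% |
| 0.25 | 2.1% |
| 0.5 | 8.3% |
| 0.75 | 18.8% |
| 0.9 | 27.0% |
| 1 | 33.3% |

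**3. Clues only from CHG effects.** An effect can point to CHG, but its absence does not establish placebo. Only two identified CHG children then fix a later place. The share halves to q²/6: 4.2% at q = 0.5 and 1.0% at q = 0.25.

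**4. Clues only from Day 7.** Assume random (exponential) gaps with mean 9.13 days. With x = 7/9.13 = 0.767:

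- P(one gap exceeds 7 days) = e^(−x) = 0.464.
- P(two gaps together exceed 7 days) = e^(−x)(1 + x) = 0.821.
- Third place, every arm revealed at Day 7: (1/3)(0.464) = 0.155.
- Fourth place: (1/3)(0.821) + (2/3)(0.464) = 0.583.
- Share: (0.155 + 0.583)/4 = 18%.
- With CHG-only clues the share is 0.1845 × q²/2: 2.3% at q = 0.5 (about 1 child of 60) and 0.6% at q = 0.25.

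**5. Clues at baseline.** If study staff hand the toothbrush and additional instruction to one arm only, the arm is visible at once for every child. Then q = 1, there is no lag, and step 1 applies in full.

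**6. Effect of varying the block size.** Simulated trials of 60, with all earlier arms known and an observer who knows the set of sizes but not the block boundaries:

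| Blocks | certain share | best guess right |
|---|---|---|
| fixed 4 | 33% | 71% |
| random 4 and 6 | about 6% | 69% |
| random 4, 6 and 8 | about 2% | 68% |

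**The case against.** Fixed small blocks behind a pharmacy-held list are a common design, and a block of four leaks nothing while allocation stays masked. The pharmacy generates the list, keeps it and dispenses the rinse. Consent comes before the rapid test and commits test-positive children to the trial. Entry then depends on a laboratory result expected to be positive in about one of four children screened, so steering a chosen child into a known slot is hard. The primary outcome is microbiological. All of this stands, and it limits the harm from selection. It does not remove discretion over whom to approach or how the judgment criteria are applied, and it does not protect the reported outcomes of Aim 2.

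A reader might infer that taste and staining reveal the drug, and hence that coordinators can foresee a third of allocations. The documents do not support this. Human Subjects lists the effects without a frequency, describes them as transient, reversible or preventable, and nowhere says that they identify the arm; the placebo uses the CHG vehicle. On that route alone the certain share is probably a few percent (steps 3 and 4). Nor is one third a ceiling: it is the average under complete knowledge of earlier arms.

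It is also fair to object that varying the blocks barely lowers the rate of correct guessing. That is so. The gain is in certainty; only keeping past allocations masked removes both.

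**Conclusion.** The point holds as an inexpensive improvement, not as evidence that concealment fails. The fixed, stated block size does no harm at q = 0. Its cost rises with q²: 2% of allocations certain at q = 0.25, 8% at q = 0.5, and 33% on average (25% to 50% in a realized trial) if every earlier arm is known. If the only clues are CHG effects reported at Day 7, the share is about 2% at q = 0.5. These figures assume that staff know the block size and that arms become known independently; the Day 7 figures also assume random arrivals.

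The more serious matter is the documents' own conflict. A toothbrush for one arm, additional instruction for one arm, and a control arm called usual care do not fit a double-blind placebo design in which allocation is not shared with staff. A reader might conclude that staff are in fact unblinded. The text does not go that far: it does not say who hands over the toothbrush, and the usual-care wording may belong to the no-therapy control that the protocol says was debated. The passages must be reconciled before the one-third figure can be either applied or dismissed. The planned sample size is unaffected.

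**What to change.** 1. Under Baseline visit, have the pharmacy generate the list in permuted blocks of randomly varying size (for example 4, 6 and 8). Hold the sizes in a pharmacy-only document, and let the protocol say only that block sizes vary and are undisclosed.
2. Reconcile the Baseline visit text on masking, the Baseline visit text on the toothbrush and usual care, and the Human Subjects text on additional instruction, so that nothing study staff hand out or explain differs by arm. This step is needed whatever is done about block size.
3. Reconcile the single-center and multi-center statements, so that it is clear one list serves the whole trial.

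The cost is a small change to the list generator and a few sentences. With blocks of up to eight, arm sizes may differ by up to four if enrollment stops mid-block, against two now, which is minor for 60 children.

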Subjects randomized to oral CHG will be provided verbal and written instruction on use of CHG oral rinse. Subjects will be asked to use CHG oral rinse twice daily for 7 days. Subjects will be educated to rinse their mouth and gargle with CHG oral rinse for 60 seconds twice a day. Subjects will be instructed to use a watch or other timing device (e.g., smartphone) to ensure that at least 60 seconds have elapses. Research staff will demonstrate the technique for all subjects using drinking water. All subjects randomized to the CHG arm will be provided a new soft bristle toothbrush to prevent recontamination of the oropharynx with *S. aureus* from a contaminated toothbrush. Subjects randomized to usual care will not be provided with any of the above. Regardless of treatment allocation, study staff will educate all subjects' parent/guardian, and subject (if of sufficient age) with the clinical significance of the results of their positive test for oropharyngeal

S. aureus colonization. More specifically, they will be educated that currently testing for *S. aureus* oropharyngeal colonization is considered experimental and that if the test is positive, the clinical significance is unclear. They will also be educated that tens of millions, perhaps over 100 million Americans are colonized in the throat with *S. aureus*, and the vast majority do not suffer consequences of having this bacteria reside in the throat. Upon request, subjects will be provided with a written copy of their results as well as a written description of the clinical significance of oropharyngeal colonization that they can share with their provider, if they wish. All subjects, regardless of treatment allocation, will be provided written and verbal information about *S. aureus* and skin infection prevention and recognition of early disease. These materials were developed for previous studies done by our group.¹⁸

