Of note, we debated whether the control group not receiving CHG should receive no therapy or a placebo oral rinse. Obviously, placebo controlled trials are of stronger study design compared to non-placebo controlled studies. More specifically, in non-placebo studies, both patients and investigators will know the treatment allocation, which can lead to bias by both subjects and the investigative team. We did have concern that oral rinses/gargling with placebo or an inert substance may affect *S. aureus* colonization. However, a 1970 investigation examined this issue using quantitative techniques. Investigators asked subjects to gargle with saline and took serial quantitative cultures. They found that gargling specimens taken at 5 minute intervals for 25 minutes showed no significant decrease in organisms concentration, with mean organism concentrations at baseline of 7.11, 6.85 at 5 minutes, and 6.92 at 25 minutes.⁹⁰ This suggests that placebo will have no ability to decolonize oropharyngeal *S. aureus* from study participants.

At the baseline visit, study coordinators will also administer a pediatric *S. aureus* risk factor survey similar to surveys used for previous *S. aureus* and MRSA epidemiologic investigations by our group.^{9,17,18,76,80,84,85} Items from this survey have been based on careful reviews of the literature on *S. aureus* risk factors and have incorporated items used previously by the CDC, Health Departments, and other investigations examining MRSA risk.^{80,84} The baseline survey will collect information about demographics, medical history, antibiotic use, and behavioral risk factors for *S. aureus* infection and colonization. Participants and their parent/guardian will be given phone numbers of the study coordinator for questions. Participants and their parent/guardian will be compensated for their time for this and all study visits.

Follow-up visits

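### As written, only the CHG arm gets a new toothbrush meant to prevent recontamination, so the Day 7 comparison is rinse plus brush against placebo rinse

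*Combined protocol and SAP*

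**What the plan says.** All of this is in the combined protocol and SAP.

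- **Brush.** Under Experimental Design and Methodology, Baseline visit: "All subjects randomized to the CHG arm will be provided a new soft bristle toothbrush to prevent recontamination of the oropharynx". Two things are explicit: the arm, and a purpose that bears directly on the primary endpoint, Day 7 eradication at the oropharynx.
- **Control arm.** The next sentence reads "Subjects randomized to usual care will not be provided with any of the above". The trial has no usual-care arm; its control is a placebo rinse made from the CHG vehicle.
- **Blinding.** The same section says "treatment allocation randomization will not be shared with either the study staff or patients". On dispensing it says "The research pharmacists will dispense the appropriate oral rinse to the participant and their parent/guardian" and mentions no brush.
- **Rinse instruction.** The section first says that participants and their parent or guardian "will be given detailed instructions on the use of the oral rinse both verbally and in a handout". It then says "Subjects randomized to oral CHG will be provided verbal and written instruction on use of CHG oral rinse" and "Subjects will be asked to use CHG oral rinse twice daily for 7 days". The technique is nonetheless demonstrated to all subjects. Human Subjects/Investigational New Drug repeats the split: extra rinse information for the intervention arm in one place, education on the rinse for everyone in another.
- **Trial question.** The Structured Abstract asks whether CHG rinse beats placebo. Limitations explains that other decolonizing agents were left out so that the effect of the rinse could be determined.

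**The concern.** A co-intervention given to one arm and aimed at the endpoint is completely confounded with treatment. With two arms and the brush tied to allocation, the Day 7 difference estimates the joint effect of rinse and brush. No covariate adjustment or sensitivity analysis can split it, and the imbalance cannot be repaired after randomization. This is the problem that Limitations says the design set out to avoid.

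The second risk is to the blind. If families or staff learn that the brush goes with CHG, they can infer the arm. That matters less for a laboratory endpoint than for self-reported adherence, tolerability and adverse events (the Visit 2 survey and Aim 2). The document does not say who hands out the brush or whether it is concealed.

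The instruction text is a lesser matter. The passages disagree and need reconciling, but they do not clearly show that unequal coaching was planned.

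**Working it through.** **Inputs from the document** (Power and Sample Size; Data Analyses and Data and Safety Monitoring): 50% versus 10% eradication, alpha 0.05, 27 per group, 85% power, 10% attrition, Fisher's exact test. The document does not state whether the test is one- or two-sided; two-sided is assumed here.

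**The plan's own figure.** With mean rate 0.30 and difference 0.40:

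- n₀ = [1.96·√(2·0.30·0.70) + 1.036·√(0.25 + 0.09)]² / 0.40² = 21.96
- With continuity correction: n = (n₀/4)·[1 + √(1 + 4/(n₀·0.40))]² = 26.7, so 27 per group and 54 in total
- With attrition: 54/0.9 = 60

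The stated sample size reproduces and is not in dispute. Full enumeration of the two-sided Fisher test at 27 per arm gives power 87.2%. The 95% half-width for the difference is 1.96·√(0.25/27 + 0.09/27) = 0.220, or about ±22 points.

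**Assumption, not in the document.** Let r be the share of cleared children who would be recontaminated by Day 7 without a new brush. The brush prevents this and does nothing else. Take r = 10%, 20% and 30%, and suppose 50% versus 10% is observed with a brush in the CHG arm only.

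- Brush in both arms: 0.50 versus 0.10/(1−r)
- Brush in neither arm: 0.50·(1−r) versus 0.10

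| r | Both arms: rates | Difference | Overstatement (40 − difference) | Neither arm: rates | Difference | Overstatement (40 − difference) |
|---|---|---|---|---|---|---|
| 10% | 50% v 11.1% | 38.9 | 1.1 | 45% v 10% | 35 | 5 |
| 20% | 50% v 12.5% | 37.5 | 2.5 | 40% v 10% | 30 | 10 |
| 30% | 50% v 14.3% | 35.7 | 4.3 | 35% v 10% | 25 | 15 |

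**Inert rinse, brush in the CHG arm only.** The rates are then 0.10/(1−r) versus 0.10. The chance of a significant Fisher result at 27 per arm is 0.7% with no brush effect, and 0.9%, 1.2% and 2.0% for r = 10%, 20% and 30%. It stays below 5% across the assumed range.

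**Outside that range.** The rejection rate reaches 5% once the brush adds about 8 points, and is 7.6%, 17% and 31% at 10, 15 and 20 points. Under the recontamination model a gain of b points needs r = 1 − 0.10/(0.10 + b). That is 44% for 8 points, and 50%, 60% and 67% for 10, 15 and 20 points. These are what-if figures for a brush effect much stronger than the one assumed above.

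**The case against.** The strongest reply is that this is residual text. The passage refers to a usual-care arm that does not exist, and later in the same section the authors write that "we debated whether the control group not receiving CHG should receive no therapy or a placebo oral rinse". Read literally, the usual-care sentence would also deny placebo children the rinse instructions that the section has already given to everyone. Elsewhere CHG seems to stand loosely for the study rinse: Follow-up visits times every participant's Visit 2 from the start of oral CHG. Study staff who do not know the allocation could not hand a brush to one arm selectively, so the conflict would probably surface at start-up. On the assumed range the bias against a both-arms comparison is small beside a ±22-point interval, and the false-positive rate stays below 5%.

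Much of this stands. The intent is uncertain, the likely effect may be small or nil, and the figures above 5% need a brush effect beyond the stated range. It does not remove the defect. The passage is current text, no other passage gives placebo children a brush, and the document does not say how the conflict between the blind and the brush would be settled. If the line is intended, it confounds the primary contrast; if it is left over, it is a wrong operating instruction. Either way it needs an edit.

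**Conclusion.** The concern holds: as written, the primary contrast is CHG rinse plus a new brush against placebo rinse, and the arm-specific item conflicts with the double-blind design. That conclusion rests on the text alone. Its size is unknown. With 10% to 30% recontamination among cleared children, an assumption without support in the document, the overstatement is 1.1 to 4.3 points against a design with brushes in both arms, and 5 to 15 points against one with none. On that range an inert rinse would not raise the false-positive rate above 5%. The point should be fixed because the protocol itself expects the brush to act on the endpoint, the imbalance cannot be undone after randomization, and the remedy is nearly free.

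**What to change.** Treat both arms alike on the brush.

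1. Baseline visit: assign the toothbrush and the verbal and written rinse instruction to all randomized subjects, with the same brush in each arm.
2. Baseline visit: in the sentences on using and gargling the rinse, replace the reference to CHG with *the study oral rinse*.
3. Baseline visit: delete the usual-care sentence.
4. Human Subjects/Investigational New Drug: give the additional rinse information to all randomized subjects and refer to the study oral rinse.
5. Follow-up visits: time Visit 2 from the start of the study oral rinse. This is for consistency and does not bear on the brush.

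Giving no brush to either arm also removes the confounding and is closer to a test of the rinse alone.

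**Cost.** About 30 more toothbrushes (none if neither arm gets one) and wording changes, with no extra visits. At the stated 50% and 10% rates the sample size is unchanged. If the brush does matter, each option costs power relative to 87.2% at 27 per arm:

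| r | Brush in both arms: power | Per arm for 85% | Brush in neither arm: power |
|---|---|---|---|
| 10% | 84.4% | 28 | 77.0% |
| 20% | 80.5% | 30 | 63.2% |
| 30% | 75.0% | 34 | 47.3% |

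If a brush in both arms raised the placebo rate to 20%, which needs r = 50%, power would be 55% and 50 per arm would be needed.
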